3.0 Inclusion and Exclusion Criteria*

Patients with gynecological cancer who are referred to receive treatment at Brigham and Women's Hospital (BWH) and/or Dana-Farber Cancer Institute (DFCI), and who will undergo routine clinical standard of care pelvic MRI, are eligible to participate in the study. Subjects with benign uterine fibroids referred to routine pelvic MRI at BWH will serve as controls.

Inclusion Criteria

- Participants with suspected or histologically confirmed diagnosis of primary or recurrent gynecological cancer including uterine endometrial, cervical, vaginal, vulvar, ovarian, and smooth-muscle tumors undergoing routine clinical standard of care pelvic MRI
- Control subjects with benign fibroids undergoing routine clinical standard of care pelvic MRI
- Age \geq 18 years
- ECOG performance status of \leq 2, based on treating physician's discretion (Appendix A)
- Ability to understand and the willingness to sign a written informed consent document

Exclusion Criteria

- Contraindication to MRI identified by the MR procedure screening form, such as a pacemaker, aneurysm clip, inner ear implant, neurostimulator, or other MR non-compatible device or implant
- Uncontrolled intercurrent illness including, but not limited to ongoing or active infection, symptomatic congestive heart failure, unstable angina pectoris, cardiac

arrhythmia, or psychiatric illness/social situations that would limit compliance with study requirements

- Adults unable to consent
- Non-english speaking subjects
- Pregnant women
- Prisoners

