11.0 Data Management* and Confidentiality

11.1 Data analysis plan and statistical procedures

Primary endpoint of this study is to evaluate the feasibility of MRF and QTI in gynecological pelvic MRI. Feasibility will be assessed in two ways. First, the aspects of image quality such as artifacts, sharpness, and noise will be evaluated by two radiologists. Second, regions-of-interest (ROI) of the tumor and normal tissue (uterine normal endometrium, myometrium, cervical stroma, ovaries) will be recorded and ROI-based parameters from MRF (T1 and T2 relaxation values) and QTI (total mean kurtosis MK_T , microscopic anisotropy MK_A , isotropic heterogeneity MK_I , fractional anisotropy FA, microscopic fractional anisotropy μFA) will be compared between the tumor and normal tissue, and between different tumor histologies. One-way analysis of variance will be used to determine the statistical difference of each MRF and QTI value between the malignant tumors, benign fibroids, and normal tissue.

Secondary endpoint is to assess the predictive and prognostic value of MRF and QTI in gynecological malignancies. For this purpose, MRF and QTI parameters from gynecological malignancies will be compared with the treatment effect

assessed by clinical examination and/or cross-sectional follow-up imaging, and the participants' outcome by means of Kaplan-Meier method with log rank test, and Cox proportional-hazards model.

Variables that will be collected include the quantitative MRI parameters, demographic information (age, sex), clinical variables (diagnosis, tumor stage, histopathologic and molecular data, laboratory results, treatment, dates of diagnosis and treatments), follow-up images, and outcome data (recurrences, survival). An Excel database including MRI and clinical variables will be developed for the purposes of this study.

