11.2 Power analysis

The sample size calculation is exploratory in nature since no protocols with MRF or QTI in gynecological imaging have been published. One prior publication reports the range of traditional T2 relaxation values in one patient with endometrial cancer [15]. Based on the average value of 78 ms T2 relaxation time in endometrial cancer, and on the assumption of 5% difference to other histologies and SD of 5 ms, the calculated targeted sample size is 27 patients per group with power set at 80% and type I error rate of 5% (www.sample-size.net/sample-size-means/).

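### Section 11.1 plans ordinary one-way ANOVA with a single pooled variance for three unlike tissue groups; a Welch test for malignant versus fibroid, and group-specific variances elsewhere, would remove the risk at almost no cost

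*Combined protocol and SAP*

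**What the plan says.** Section 11.1 states the method in one sentence: "One-way analysis of variance will be used to determine the statistical difference of each MRF and QTI value". The comparison it sets up is "between the malignant tumors, benign fibroids, and normal tissue", so the test has three groups, and it is repeated for T1, T2 and five QTI metrics. Section 11.1 gives no unequal-variance form, variance check, transformation or follow-up contrast. It also does not say how many normal-tissue values enter the ANOVA.

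Two of the three groups are composite. Section 11.1 lists "normal tissue (uterine normal endometrium, myometrium, cervical stroma, ovaries"), which is four sites. Section 3.0 admits cancers "including uterine endometrial, cervical, vaginal, vulvar, ovarian, and smooth-muscle tumors", primary or recurrent. Fibroids are one benign entity.

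The only SD in the documents is in Section 11.2, which makes an "assumption of 5% difference to other histologies and SD of 5 ms" for T2. Section 23.0 allots 27 women with malignancy and 27 with fibroids to each sequence.

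**The concern.** Ordinary one-way ANOVA uses one within-group variance, averaged over the groups in proportion to their degrees of freedom. If the groups differ in spread, that average is wrong for any particular pair. If they also differ in number of values, it is wrong for the overall F test. The make-up of the groups gives reason to doubt equal spread: a mixture of entities with different means has a larger SD than its components. The numbers may be unequal too, because one woman can supply several normal regions of interest.

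This analysis serves the primary endpoint. Section 11.2 sets 80% power and a 5% type I error rate, and an error term unsuited to the comparison could deliver neither. The direction matters. A more variable normal group hides real differences between cancer and fibroid, whereas a more variable malignant group produces false positives.

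**Working it through.** **Step 1: reproduce the plan's figure.** Section 11.2 gives a mean of 78 ms, a 5% difference and an SD of 5 ms, so the difference is 0.05 × 78 = 3.9 ms. The normal approximation gives n = 2 × (1.960 + 0.842)² × 5² / 3.9² = 25.8. The two-sided two-sample t calculation gives 26.8, hence 27 per group (power 80.3% at 27, 78.8% at 26). The stated 27 is reproduced. It rests on two groups with a common SD.

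**Step 2: assumptions.** The documents give no SD for fibroids, for any normal tissue, for T1 or for any QTI metric. I therefore assume a baseline SD of 5 ms and double it in one group at a time. The number of normal values is also assumed: 27 (one per cancer participant), 54 (one per woman in both arms of a sequence) or 108 (four sites in 27 women). Values are treated as independent.

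**Step 3: why the F test depends on the counts.** With no true difference, the expected between-group mean square is Σ(1 − nᵢ/N)σᵢ²/(k − 1), and the expected error mean square is Σ(nᵢ − 1)σᵢ²/(N − k). The test is roughly right when their ratio is near 1.

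- 27/27/27, normal SD 10 ms: (2/3)(25 + 25 + 100)/2 = 50, against 26 × 150/78 = 50. Ratio 1.00.
- 27/27/108, normal SD 10 ms: [(5/6)(25 + 25) + (1/3)(100)]/2 = 37.5, against (26 × 50 + 107 × 100)/159 = 75.5. Ratio 0.50, so the test is conservative.
- 27/27/108, malignant SD 10 ms: [(5/6)(100 + 25) + (1/3)(25)]/2 = 56.25, against (26 × 125 + 107 × 25)/159 = 37.3. Ratio 1.51, so the test is anti-conservative.

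**Step 4: the pooled contrast at 27 per group, normal SD 10 ms.** The pooled SD is √50 = 7.07 ms, so the contrast's standard error is taken as 7.07 × √(2/27) = 1.92 ms. The true standard error is 5 × √(2/27) = 1.36 ms. The rejection threshold is 1.99 × 1.92 = 3.83 ms. Power for 3.9 ms is then P(Z > (3.83 − 3.9)/1.36) = 52%.

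**Step 5: simulation results** (at least 40,000 runs per cell; contrast power is for a true difference of 3.9 ms).

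| Group with SD 10 ms (others 5) | Normal values | Share of error df from normal tissue | F test, type I error | Pooled contrast, type I error | Pooled contrast, power |
|---|---|---|---|---|---|
| None (all 5) | 27 | 33% | 5% | 5% | 81% |
| Normal | 27 | 33% | 6% | 0.7% | 52% |
| Normal | 54 | 50% | 2% | 0.2% | 40% |
| Normal | 108 | 67% | 0.4% | 0.1% | 30% |
| Malignant | 27 | 33% | 6% | 8% | – |
| Malignant | 54 | 50% | 9% | 10% | – |
| Malignant | 108 | 67% | 14% | 13% | – |

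The Welch t-test for malignant versus fibroid holds about 5% type I error in every row. It has about 80% power whenever those two groups have an SD of 5 ms. If the malignant SD really is larger, no valid test recovers the planned power.

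**Step 6: what the plan's own figure implies.** Two histologies 3.9 ms apart in equal shares add variance 3.9²/4 = 3.80, so the malignant SD becomes √(25 + 3.80) = 5.37 ms. Differences of 3.9 ms in both directions give at most √(25 + 15.21) = 6.34 ms. With 27 per group, the contrast's type I error is 5.3% and 5.9% respectively, and the F test stays at about 5%.

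**The case against.** The strongest reply is that the larger errors belong to a test the plan does not contain. Section 11.1 names an overall three-group ANOVA and no pooled follow-up contrast. Nor does it single out malignant versus fibroid as the primary comparison; it names tumor versus normal tissue and comparisons between histologies as well. At 27 values per group the test that is named moves by only about one point. The SDs and the counts of normal values are my assumptions, and the plan's own 5% difference supports an SD nearer 5.4 ms than 10 ms. Unequal variances can also partly cancel: with malignant and normal both at 7.5 ms and 27 per group, the contrast has 3.9% type I error and the F test 5.2%. This is a pilot, and its sample size is described as exploratory.

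All of that stands, and it limits the size of the point without removing it. A three-group F test cannot say which groups differ, so a malignant-versus-fibroid comparison has to follow, and the plan leaves its error term open. It also leaves open the number of normal values, on which the F test depends.

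A reader might infer more than this, in two ways. One is that the ANOVA has eleven groups; it has three, and the tumor types and tissues are components of two of them. The other is that normal-tissue spread sets the error term for cancer versus fibroid. With 27 normal values it supplies one third of the error degrees of freedom, and it dominates only if several sites per woman are entered separately, which the plan does not say.

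**Conclusion.** The point holds as a gap worth closing, not as a demonstrated error. Equal variance is doubtful given how the groups are composed, but the documents cannot show that variances differ, by how much or in which direction. Under an assumed twofold SD ratio:

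- The planned F test is nearly unaffected at 27 per group and becomes unreliable only when normal values outnumber the lesion values.
- A contrast using the pooled error is unreliable even at 27 per group.

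At the heterogeneity implied by Section 11.2 itself, both effects are small. All these figures assume independent values. Tumor and normal values from the same woman are not independent, and the calculation does not cover that.

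**What to change.** In Section 11.1:

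1. Compare malignant with fibroid for each parameter by a Welch two-sample t-test with a 95% CI, using one value per woman and only those two groups' variances. This is sound because the two groups are different women.
2. For comparisons that include normal tissue from the same women, use a mixed model with a participant effect and a separate residual variance for each tissue group. Welch ANOVA alone does not handle values from the same woman, so reserve it for comparisons of independent groups.
3. State how many normal-tissue values per woman enter each analysis.

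The cost is one or two sentences and no extra participants. If all variances are in fact equal, simulated power for malignant versus fibroid at 27 values per group is 80.9% with the pooled error and 80.4% with Welch, a loss of 0.5 percentage points.

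### The three-level ANOVA has no organ or participant term, so organ of origin is substantially confounded with malignancy

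*Combined protocol and SAP*

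**What the plan says.** Section 11.1 states: "One-way analysis of variance will be used to determine the statistical difference of each MRF and QTI value", the comparison being "between the malignant tumors, benign fibroids, and normal tissue". It names no organ factor, covariate, blocking or participant term.

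The three groups are made up as follows.

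- **Malignant.** Section 3.0 admits suspected or confirmed "gynecological cancer including uterine endometrial, cervical, vaginal, vulvar, ovarian, and smooth-muscle tumors". That is five anatomical sites plus one tissue type. Section 23.0 sets one malignancy group of 27 per sequence, with no quota by site.
- **Benign.** Section 3.0: "Subjects with benign uterine fibroids referred to routine pelvic MRI at BWH will serve as controls". This is one lesion type from one organ, again 27 per sequence.
- **Normal.** Section 11.1: "regions-of-interest (ROI) of the tumor and normal tissue (uterine normal endometrium, myometrium, cervical stroma, ovaries) will be recorded". Section 23.0 lists no healthy volunteers, so these regions come from the same women who supply the tumours and fibroids.

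Section 11.1 also says that the parameters "will be compared between the tumor and normal tissue, and between different tumor histologies". It gives no test, pairing rule or group size for the histology comparison.

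**The concern.** The three groups differ in organ mix as well as in malignancy, and a one-way model cannot separate the two. An ovarian or cervical cancer is set against a uterine smooth-muscle lesion and against normal tissue that may come from other organs. A difference in T1, T2 or a diffusion parameter between those organs would then show up as a difference between malignant and benign.

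The second problem is dependence. Tumour and normal regions from one woman share her scanner session and physiology. One-way ANOVA treats them as independent, which discards the within-woman information that would sharpen the tumour-versus-normal contrast.

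What is at stake is interpretation. Section 1.0 includes comparison of parameters between tumour entities and normal structures in the primary objective, and makes comparison with normal structures and fibroids part of the secondary diagnostic objective. A significant F test from this model could not be attributed to malignancy.

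**Working it through.** **Inputs.** Section 11.2 gives a T2 mean of 78 ms in endometrial cancer, a 5% difference to other histologies, SD 5 ms, 80% power and 5% type I error. Section 23.0 gives 27 per group. Two-sided testing is assumed because sidedness is not stated. The documents give no organ differences, no within-woman correlation and no planning values for the QTI parameters, so everything below is on the T2 scale.

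**Plan's own figure.** The difference is 0.05 × 78 = 3.9 ms, so the standardised effect is 3.9/5 = 0.78. The two-sample t calculation gives 26.8, rounded up to 27, with 80.3% power. The stated 27 reproduces.

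**Illustration of the confounding.** Assume no effect of malignancy. A share *s* of the cancers comes from organs whose T2 lies 3.9 ms away from that of fibroids. The apparent malignant-fibroid difference is 3.9*s*. The malignant variance is 25 + *s*(1 − *s*) × 3.9², and the standard error is √[(malignant variance + 25)/27]. The probability of significance is approximately P(Z > 2.007 − difference/SE), where 2.007 is the t critical value on 52 degrees of freedom.

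| Share *s* | Difference (ms) | SE (ms) | Ratio | Approximation | Simulation |
|---|---|---|---|---|---|
| 1/2 | 1.95 | 1.41 | 1.38 | 27% | about 28% |
| 3/4 | 2.93 | 1.40 | 2.09 | 53% | about 53% |
| all | 3.90 | 1.36 | 2.87 | 80% | 80% |

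The last row restates the design power, as it must. Half of 27 is not a whole number; 14 of 27 gives 28%.

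**The three-level ANOVA itself.** This was simulated with 27 per level and no malignancy effect. Cancers were spread over the six entities and normal regions over the four tissues as evenly as 27 allows, and all non-myometrial tissue was shifted by the same amount.

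| Organ shift | ANOVA rejects | Malignant-fibroid t test rejects |
|---|---|---|
| 0 ms | 5% | 5% |
| 2 ms | 20% | 23% |
| 3.9 ms | 61% | 65% |

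With the 3.9 ms shift, 23 of the 27 cancers are non-myometrial, giving a spurious difference of 3.9 × 23/27 = 3.3 ms.

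**Within-woman alternative.** The SD of tumour minus own normal region is 5√[2(1 − ρ)], which is 7.07, 5.92 and 5.00 ms at ρ = 0, 0.3 and 0.5. The table shows power for 3.9 ms.

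| Contrast | ρ = 0 | ρ = 0.3 | ρ = 0.5 |
|---|---|---|---|
| Paired tumour v own normal, 27 women | 79% | 91% | 97% |
| Paired tumour v own normal, 20 women | 65% | 80% | 91% |
| Malignant v fibroid on organ-referenced differences, 27 v 27 | 51% | 66% | 80% |
| The same, 20 v 27 | 45% | 59% | 73% |

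The unadjusted malignant-fibroid test has 80% power. Referencing both groups to their own organ therefore costs power on that contrast unless ρ reaches about 0.5.

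**The case against.** **This is a pilot whose primary endpoint is feasibility.** Section 15.0 calls it a pilot, section 11.2 calls the sample size exploratory, and image quality is the first feasibility measure. This has weight. A reader might infer that the study cannot answer its own question, and the documents do not support that: the image-quality assessment is untouched. The ANOVA is nevertheless the only test named for the parameter comparisons, which are the second feasibility measure.

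**The plan may not intend to collapse the normal tissues.** Section 11.1 names four tissues, and section 1.0 refers to normal structures in the plural. A reader might infer that they definitely form one level. The text does not say so; it names three groups and leaves the levels undefined. The need to define them stands.

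**A histology comparison is also planned.** It has no stated test, and it compares tumours with one another. It does not adjust the ANOVA.

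**The organ shifts are invented.** The 3.9 ms is the plan's assumed difference between histologies, not an organ difference. The percentages are therefore illustrations. The confounding follows from the composition of the groups, but its size does not.

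**Confounding is not complete.** Smooth-muscle malignancies and normal myometrium share a tissue with fibroids, and endometrium, cervix and ovary can appear among both tumours and normal regions. This is correct, and it is why an organ-matched contrast is possible at all.

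**Conclusion.** The point holds for the analysis model. As written, the ANOVA mixes organ of origin with malignancy and ignores that regions come from the same women, so a significant result cannot be attributed to malignancy alone. The distortion could be negligible or large. With a 2 ms organ shift and an even spread of entities, the ANOVA rejects in about 20% of studies against a nominal 5%; with 3.9 ms it rejects in about 61%. These figures rest on an assumed shift, SD 5 ms, the assumed site mix and T2 only.

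A reader might also infer that the sample size is wrong or that new control groups are needed. Neither follows. The 27 per group is arithmetically correct for a two-group comparison, and the relevant types of normal region are already to be recorded.

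Restricting malignant versus fibroid to tumours of the uterine body might look like a remedy. It would still set endometrial cancers against smooth-muscle lesions, so tissue of origin would stay confounded, and an unknown share of the 27 would remain.

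**What to change.** Amend section 11.1 as follows.

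1. Make tumour versus normal a within-woman comparison of the tumour with her own normal region of the same organ where one is recorded, by a paired test or a mixed model with a participant term.
2. Define the levels explicitly and keep endometrium, myometrium, cervical stroma and ovary separate.
3. Report malignant versus fibroid descriptively, by tumour entity, and state that a difference is not attributable to malignancy alone. Use the organ-referenced difference only as a sensitivity analysis, given its lower power at correlations below about 0.5.
4. Describe separately the tumours with no matching normal region: vaginal and vulvar tumours, and those whose organ has been removed or replaced by tumour.

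The change is to analysis wording. It needs no new participants, scans or types of region. The cost is that women without a matching region leave the paired comparison. Section 3.0 admits recurrent disease and sites with no listed normal counterpart, and section 11.1 does not say that every woman contributes every tissue. The number lost cannot be predicted from the documents; the 20-woman power figures show one possible case.

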1.0 Objectives*

Magnetic Resonance Fingerprinting (MRF) and Q-space Trajectory Imaging (QTI) are advanced new magnetic resonance imaging (MRI) sequences that provide rapid quantitative tumor metrics and enable visualization of the tumor microstructure, respectively. This would have substantial value in diagnostics and tumor characterization in cases such as insufficient biopsy specimens, MRI-guided treatment planning, and in evaluating treatment response and differentiating residual tumor from treatment related changes. Furthermore, quantitative metrics from MRF and QTI may provide prognostic or predictive biomarkers that guide the proper oncologic workup and treatment for the patient. We hypothesize that QTI provides deeper insight into the tissue microstructural environment and that quantitative metrics from QTI and MRF accurately characterize the gynecological malignancy in comparison with the tumor histology. Furthermore, we hypothesize that MRF and QTI provide prognostic information valuable to the patient and treating physician.

Primary Objective

- to investigate the feasibility of advanced MRI sequences in participants with gynecologic malignancy and in control participants with benign uterine fibroids by measures of image quality and by comparing the MRI parameters between different tumor entities and normal anatomic structures

Secondary Objectives

- to study the diagnostic value of MRF and QTI in characterizing the tumor by comparing the tumor parameters with normal structures, benign fibroids, and tumor histology
- to study the prognostic value of MRF and QTI by comparing tumor parameters with treatment effect and participant outcome

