sequences (QTI and MRF). Scanning time will be increased with 10–15 minutes which may cause discomfort to participants due to laying on the scanning table for a longer period of time.

Follow-up data including treatment outcome, tumor histology, clinical variables, laboratory results, medical images, and survival data, will be collected from the participant's electronic medical records. For survival data, the duration of follow-up is up to 4 years after participation and the MRI scan with new MRI methods.

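### Does Section 11.1 need to say whether log-rank or Cox decides the prognostic analysis, and in what form each MRI parameter enters?

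*Combined protocol and SAP*

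**What the plan says.** Section 1.0 lists as a secondary objective "to study the prognostic value of MRF and QTI by comparing tumor parameters with treatment effect and participant outcome", and says that "quantitative metrics from MRF and QTI may provide prognostic or predictive biomarkers that guide the proper oncologic workup and treatment for the patient". Section 11.1 repeats the aim: "Secondary endpoint is to assess the predictive and prognostic value of MRF and QTI in gynecological malignancies".

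The variables are "ROI-based parameters from MRF (T1 and T2 relaxation values) and QTI", the latter giving five measures (MK_T, MK_A, MK_I, FA, μFA). All seven are continuous. The survival method is one phrase: parameters are compared with the participants' "outcome by means of Kaplan-Meier method with log rank test, and Cox proportional-hazards model". Recurrences and survival are both to be collected. On the horizon, Section 9.0 says: "For survival data, the duration of follow-up is up to 4 years after participation".

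Section 23.0 gives 27 women with malignancy for MRF and 27 for QTI, and Section 9.0 gives each woman one sequence. The prognostic data are therefore two parameters in one set of 27 and five in another. Section 8.0 only points back to the objectives, and Section 11.2 sizes a comparison of mean T2. No section ranks the two tests, states the form of the Cox covariate or gives a grouping rule.

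**The concern.** A log-rank test on a continuous measurement needs groups, and Cox does not. If women are split at the median for log-rank and the raw value goes into Cox, the same parameter gets two p-values that can fall on opposite sides of 5%. With few events this would happen often, and the plan does not say which result stands.

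Two harms could follow. If log-rank decides, or Cox is fed the split value, power is lost when risk rises steadily with the parameter. If whichever test is significant is reported, false positives increase. Because Section 1.0 presents these metrics as possible biomarkers to guide treatment, it is fair to ask whether a claim of prognostic value could turn on an unstated choice.

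**Working it through.** **1. The plan's own figure.** Section 11.2 assumes a T2 of 78 ms, a 5% difference, an SD of 5 ms, 80% power and 5% type I error. The difference is 0.05 × 78 = 3.9 ms. By the normal approximation, n = 2 × (1.960 + 0.842)² × 5² / 3.9² = 25.8, so 26 per group. The two-sided t test has 78.8% power at 26 and 80.3% at 27. The stated 27 is reproduced, but it says nothing about survival.

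**2. Events.** The documents give no event rate. Assuming 30, 40 or 50% with an event by 4 years: 27 × 0.30 = 8.1, 27 × 0.40 = 10.8, 27 × 0.50 = 13.5.

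**3. Simulation.** 27 women, exponential times, censoring at 4 years, two-sided 5% tests, and a normal parameter unless stated. Cox uses the continuous value with a likelihood-ratio test. Log-rank uses a 14/13 median split. Each power scenario has 20,000 to 30,000 runs and the null has 30,000 to 40,000.

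No true effect, across the three event rates:

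| Rule | Type I error |
|---|---|
| Continuous Cox | 5.5-5.8% |
| Median-split log-rank | 4.9-5.6% |
| Either test accepted | 8.3-8.8% |

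The excess is about 3 points per parameter. Over seven parameters and one outcome, expected false positives go from 7 × 0.056 = 0.39 to 7 × 0.086 = 0.60, or 0.21 more in the whole study.

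Graded effect, at 30/40/50% events:

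| HR per SD | Cox power | Log-rank power | Either | Tests disagree |
|---|---|---|---|---|
| 1.5 | 21/25/30% | 14/17/20% | 26/30/35% | 15-19% |
| 2.0 | 47/57/66% | 29/37/44% | 51/61/69% | 25-29% |

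Most disagreement is Cox significant and log-rank not. At HR 2, log-rank alone is significant in only 50.7 − 46.8 = 3.9, 60.8 − 57.3 = 3.5 and 69.0 − 66.0 = 3.0 points of runs. A separate run with the Cox score test agrees: at HR 2 and 30/50% events, 50/67% against 31/46%.

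**4. How far this depends on the model.** A normal parameter with a log-linear effect favors continuous Cox. Two alternatives:

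- Lognormal parameter entered untransformed, 30/50% events. At HR 1.5, Cox has 18.6/25.4% and log-rank 13.4/19.8%, a lead of 5.2/5.6 points. At HR 2, 40.9/57.6% against 28.4/43.0%, a lead of 12.5/14.6 points.
- Step at the median, HR 4. Cox has 30/40/50% and log-rank 33/44/54%, so log-rank is ahead by 3 to 5 points.

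**5. What ranking Cox first would leave untouched.**

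- Multiplicity: over the five QTI parameters with no true effect, the chance of at least one significant result is 14-26% for Cox alone (correlation 0.8 down to 0), against 23-36% if either test counts.
- Scale: if a skewed parameter may be transformed after inspection, accepting raw or log Cox gives 8.0/7.9% under the null (log-SD 0.8, 30/50% events), against 6.4/6.0% for raw and 5.6/5.5% for log alone. That is nearly the inflation that the ranking is meant to prevent.
- Case mix: Section 3.0 admits women with "suspected or histologically confirmed diagnosis of primary or recurrent gynecological cancer" across several tumor types. With two types, 40% events, no effect within type and parameter shifts of 0.5-1 SD, continuous Cox is significant in 6-8% of runs at a between-type HR of 2 and in 8-15% at an HR of 4.

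**The case for a change.** The case for a change is that it costs one paragraph and no data, and closes a route to choosing the test after seeing results. No section labels the survival analyses descriptive; the pilot label in Section 15.0 and the exploratory label in Section 11.2 are attached to other matters. A cut-point searched for in the data would give 26-27% false positives for one parameter, and the plan does not exclude that.

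The silence is real, and neither missing text nor redaction explains it. The simulated figures are also reproducible under their assumptions. But a searched cut is not proposed, and a plan should not be charged with every practice it fails to forbid. The plan likewise does not say that either p-value may be claimed, that both tests will be run on every parameter, or that log-rank will be applied to split MRI values and not to clinical groups. Kaplan-Meier with log-rank alongside Cox is a conventional pairing, one for display and one for estimation. A short clarifying sentence would do no harm, but it would not make the prognostic results confirmatory, because few events, several parameters and mixed tumor types would remain.

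**Conclusion.** No change is needed. Section 11.1 leaves the priority of the tests, the Cox covariate form and the log-rank grouping unstated, but it names suitable methods and contradicts nothing. An analyst would ordinarily enter each parameter as a continuous Cox covariate, report a hazard ratio with its confidence interval for every parameter, and draw Kaplan-Meier curves at the median for illustration. The existing text permits this.

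The worst plausible reading, accepting either test, costs about 3 points of type I error per parameter (about 5.6% to 8.6%). Letting a median-split log-rank decide costs roughly 7 to 10 points of power at HR 1.5 per SD and 18 to 22 at HR 2. These figures assume 27 evaluable women per sequence, full 4-year follow-up, 30-50% events and a log-linear effect of a normal parameter. None of the event rates, hazard ratios or distributions comes from the documents. Other shapes of effect shrink the power gap or reverse it.

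The analysis is secondary, the study is a pilot, and neither the primary aim nor any participant's care within the study depends on it. Readers should treat the prognostic findings as exploratory whichever test is quoted.
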